## 9.2 Sample Size/Accrual Rate

The maximum total of 42 patients will be accrued. With the estimated accrual rate of 2-3 patients per month, the maximum accrual time including DLT observation period will be around 18-24 months.

## PLANNED ENROLLMENT REPORT

Racial Categories	Ethnic Categories				Total
	Not Hispanic or Latino		Hispanic or Latino		
	Female	Male	Female	Male	
American Indian/ Alaska Native	0	0	0	0	0
Asian	0	0	0	0	0
Native Hawaiian or Other Pacific Islander	0	0	0	0	0
Black or African American	4	4	0	0	8
White	12	16	3	3	34
More Than One Race	0	0	0	0	0
Total	16	20	3	3	42

PHS 398 / PHS 2590 (Rev. 08/12 Approved Through 8/31/2015)

OMB No. 0925-0001/0002

### 9.3 Analysis of Secondary Endpoints

Every report of our secondary objectives (listed above in Section 1.2) will contain all patients included in the study. For the response calculation, the report will contain at least a section with all eligible patients. Another section of the report may detail the response rate for evaluable patients only. However, a response rate analysis based on a subset of patients will explain which patients were excluded and for which reasons. 95% confidence limits will be given.

Data that are collected serially over time will be explored graphically using box plots and/or individual time plots as well as analytically with either repeated measures analysis of variance or Friedman's nonparametric test. This trial will form the basis for a follow up proposal to examine this combination in a phase 1 study in newly diagnosed AML patients with *TP53* mutations.

We will assess MRD by measuring the mutational burden with variant allele frequency, cytogenetics, and flow cytometry before and after response is achieved to see if there is a change in any of these MRD assessment parameters. We will compare these three MRD tests at the same time points to characterize the importance of different MRD tests in different molecular subsets of AML. We will also evaluate MRD status at each time point in relation to disease outcome using chi square test of independence. This will allow us to determine which MRD assessment(s) performed at which timepoint(s) is most meaningful and helpful in determining relapsed/refractory AML outcomes. For T-Cell response and DNA methylation studies, analyses

of the data will be primarily descriptive in nature given the relatively small sample size.

Plasma venetoclax and serum nivolumab concentration-time profiles will be analyzed by non compartmental analysis in Phoenix Winonlin, and subsequently by population mixed effects PK modeling using NONMEM. Pharmacokinetic parameters (e.g., Cmax, AUC, CL, V, and t1/2) will be estimated. For venetoclax PK, concurrent antifungal medications will be grouped as strong (e.g., posaconazole, voriconazole) or moderate (e.g., fluconazole, isavuconazole) CYP3A4 inhibitors, or OATP1B1 inhibitors (e.g, micagungin) and included as a covariate in the venetoclax population PK model. Associations between: 1) antifungal drug administered and/or venetoclax exposure and changes in OATP1B1 plasma biomarkers from baseline to post-treatment; and 2) drug exposure parameters such as Cmax and AUC with toxicity or response will be performed using standard t-tests or Wilcoxon rank sum tests and illustrated using boxplots or other graphical displays. Values will be log transformed as appropriate to reflect biologic plausibility assessment.

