## SCHEMA

Induction treatment (28 day cycle up to 3 cycles) will include the following:  
Nivolumab (N) at 240mg on Day 15 for cycle 1 and Days 1 and 15 for cycles 2-3.  
Decitabine 20 mg/m^2 intravenously on Days 1-10 for up to 3 cycles.  
Venetoclax (V) 100mg PO on Day 1, 200mg on Day 2, 400mg on Days 3-28 of cycle (and cycle 2-3 of induction if needed).  
If CR, CRI, or CRh is achieved during cycles 1-3, patients will proceed with maintenance at the time response is noted.  
If no response is achieved by cycle 3, patients will come off study.  
Bone marrow biopsy will occur on Day 28 (+/- 2 days) for up to 3 cycles to determine treatment response.

Maintenance treatment (28 day cycle) for patients achieving CR or CRI will include the following:  
Nivolumab (N) will be given on Days 1 and 15.  
Decitabine (D) 20 mg/m^2 intravenously on Days 1-5.  
Venetoclax (V) 400mg po daily on Days 1-21.  
Treatment will continue until one of the following occurs: loss of response/disease progression, bone marrow/stem cell transplantation, unacceptable toxicities, or patient withdrawal

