## 6.5 Duration of Therapy

In the absence of treatment delays due to adverse event(s), treatment may continue until one of the following criteria applies:

- Disease progression/loss of response
- Bone marrow/stem cell transplantation
- Intercurrent illness that prevents further administration of treatment
- Unacceptable adverse event(s)
- Patient decides to withdraw from the study
- General or specific changes in the patient's condition render the patient unacceptable for further treatment in the judgment of the investigator
- Clinical progression
- Patient non-compliance
- Pregnancy
  - All women of child bearing potential should be instructed to contact the investigator immediately if they suspect they might be pregnant (e.g., missed or late menstrual period) at any time during study participation.
  - The investigator must immediately notify CTEP in the event of a confirmed pregnancy in a patient participating in the study.
- Termination of the study by sponsor
- The drug manufacturer can no longer provide the study agent

The reason(s) for protocol therapy discontinuation, the reason(s) for study removal, and the corresponding dates must be documented in the Case Report Form (CRF).

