g: Adverse event evaluation: will occur on Days 1 and 15 of every cycle and End of Treatment/Relapse

h: Pregnancy test will occur for women of childbearing potential at Screening and the beginning of each cycle of treatment

i: Bone marrow biopsies will occur at the end of each cycle of induction, then every 3 cycles (starting with cycle 6) and at relapse/EOT.

j: Please see study sample collection table at Section 5.1 and 11.1 for bone marrow and peripheral blood collection time details.

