### 11.1 Correlative collection calendar

Time Point	Correlative	Bone Marrow collection	Peripheral Blood Collection
Baseline			
Correlatives: Flow cytometry, Cytogenetics, Next-generation sequencing, Tetramer Analysis, and DNA methylation		X	X
Day 28 +/- 1 day of cycles 1, 2, and 3			
Correlatives: Flow cytometry, Cytogenetics, Next-generation sequencing, Tetramer Analysis, and DNA methylation		X	X
Day 28 +/- 1 day every 3 cycles starting with cycle 6 (ex. Cycles 6, 9, 12...)			
Correlatives: Flow cytometry, Cytogenetics, Next-generation sequencing, Tetramer Analysis, and DNA methylation		X	X
Day 28 +/- 1 day of end of every cycle starting with cycle 4 (excluding cycles 6, 9, 12... as above)			
Correlatives: DNA methylation			X
End of Treatment/Relapse			
Correlatives: Flow cytometry, Cytogenetics, Next-generation sequencing, Tetramer Analysis, and DNA methylation		X	X

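### Section 9.3's repeated-measures ANOVA or Friedman test, if run past cycle 3, keeps only responders still on treatment and discards other patients' early samples; a mixed model over baseline to cycle 3 avoids this.

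*Combined protocol and SAP*

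**What the plan says.** Section 9.3 (Analysis of Secondary Endpoints) plans box plots and individual time plots for serial data, and to examine them "analytically with either repeated measures analysis of variance or Friedman's nonparametric test". It names no time points, missing-data rule or mixed model for these markers. The only mixed model is for venetoclax and nivolumab pharmacokinetics: "population mixed effects PK modeling using NONMEM".

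Three other statements decide who can contribute a full series:

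- **Exit rule.** The Schema says: "If no response is achieved by cycle 3, patients will come off study". Section 9.1 agrees. Section 6.5 also ends treatment for "Disease progression/loss of response", transplantation, unacceptable toxicity, withdrawal and other reasons.
- **Marrow schedule.** Section 11, footnote i: "Bone marrow biopsies will occur at the end of each cycle of induction, then every 3 cycles (starting with cycle 6) and at relapse/EOT". Sections 5.1 and 11.1 list marrow at Day 28 of cycles 1, 2 and 3, without tying it to induction, and then at cycles 6, 9, 12 and on.
- **Blood schedule.** Sections 5.1 and 11.1 add blood for methylation at the end of the other cycles from cycle 4.

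Section 9.3 also limits the reach of the sentence on serial data. It calls the T-cell and methylation analyses "primarily descriptive in nature given the relatively small sample size". It gives MRD a comparison before and after response, and chi-square tests against outcome at each time point. On secondary objectives it promises: "Every report of our secondary objectives (listed above in Section 1.2) will contain all patients included in the study". MRD is secondary objective 1.2.6.

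**The concern.** Friedman's test ranks the time points within each patient, so a patient lacking one of them cannot enter. Classical repeated-measures ANOVA also needs a balanced table and deletes incomplete patients. Here the gaps are not accidental. The exit rule removes patients because they did not respond, and response is what variant allele frequency, cytogenetics and flow cytometry are collected to measure (Section 5.6 gives their purpose as assessing depth of response).

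If one test spans baseline to cycle 6, two things follow. The estimated change over time becomes the change in responders who have also not relapsed, been transplanted or withdrawn. And mandatory early marrow samples from everyone else go unused, which sits badly with the promise that secondary reports contain all patients.

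**Working it through.** **1. The plan's own figures.** The plan gives no sample size or power for the serial markers. Its only design calculation is the response rule in Section 9.1 (13 or more responses out of 30, 30% against 50%). Exact binomial sums give P(X ≥ 13 | 30, 0.30) = 0.0845 and P(X ≤ 12 | 30, 0.50) = 0.1808. These match the stated 0.084 and 0.181, so N = 30 and the 30% and 50% rates are used below.

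**2. How many patients can have a complete series to cycle 6.** Expected number = N × response rate × share of responders still sampled at cycle 6. The share is an assumption, since the documents give none. The 42% rate is the CR/CRi rate in the 10-day decitabine plus venetoclax cohort of Section 2.4.1: (13 + 10)/55 = 0.42.

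| N | Response rate | 100% sampled | 80% | 50% |
|---|---|---|---|---|
| 30 | 30% | 9.0 | 7.2 | 4.5 |
| 30 | 42% | 12.6 | 10.1 | 6.3 |
| 30 | 50% | 15.0 | 12.0 | 7.5 |
| 42 | 30% | 12.6 | 10.1 | 6.3 |
| 42 | 50% | 21.0 | 16.8 | 10.5 |

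For example, 30 × 0.30 × 0.50 = 4.5 and 30 × 0.50 × 1.00 = 15.0. So 15% to 50% of patients remain, all of them responders. With N = 30, 30% response and 80% sampled, the inclusion probability is 0.30 × 0.80 = 0.24, and P(X ≤ 9 | 30, 0.24) = 0.84. Fewer than 10 complete series is then the likely outcome. The documents do not say whether MLFS or PR counts as response for the cycle 3 exit. If a broader definition gave the 62% overall response rate of the same cohort, the N = 30 range would be 9.3 to 18.6.

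**3. Losses before cycle 3.** A complete-series test over baseline to cycle 3 still drops anyone who leaves before cycle 3. It may also drop early responders. Under footnote i of Section 11, a patient who enters maintenance after cycle 1 or 2 has no further induction marrow until cycle 6; under Sections 5.1 and 11.1 the cycle 2 and 3 samples are still due.

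**4. What dropping non-responders does to the cycle 3 result (illustration).** Suppose the marker changes by -1.2 at cycle 3 in responders and 0 in non-responders, and 80% of responders are sampled at cycle 6. The all-patient change is the response rate × -1.2, while the complete series contain only responders. With 300 simulated trials of 30 patients:

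| Response rate | True all-patient change | Complete series only | Mixed model, all samples | Patients with complete series |
|---|---|---|---|---|
| 30% | 0.30 × -1.2 = -0.36 | -1.21 | -0.36 | about 7 |
| 50% | 0.50 × -1.2 = -0.60 | -1.18 | -0.59 | 12 |

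No sample before cycle 6 was missing in this simulation, so the mixed model simply equals the all-patient mean at cycle 3. The gain comes from keeping the patients.

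**5. What a model can and cannot do at cycle 6 (illustration).** Assume a mean slope of -0.15 per cycle (SD 0.15), random-intercept SD 0.7 and residual SD 0.4. The true cycle 6 change is 6 × -0.15 = -0.90. Response depends on the observed cycle 3 change through a logistic curve, and 60% of responders are sampled at cycle 6 (30 × 0.50 × 0.60 = 9 complete at 50% response). Reruns with different logistic slopes and response rates of 30% to 50% gave:

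- Complete series only: -1.03 to -1.69, which is 14% to 88% too large (1.03/0.90 = 1.14; 1.69/0.90 = 1.88).
- Mixed model, time as factor, random intercept only: -1.07 to -1.18, still 19% to 31% too large.
- Mixed model with random intercept and slope: about -0.90, but this form matches how the data were generated, and fits at n = 30 often gave convergence warnings.
- If non-responders' markers rebound by 0.9 after cycle 3, the truth becomes -0.44, and random-slope models still return about -0.89.

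**The case against.** The strongest reply is that the plan does not commit to the harmful analysis. Section 9.3 never says one test must run through cycle 6, and over baseline to cycle 3 non-responders who complete three cycles stay in. Repeated-measures ANOVA is not explicitly a complete-series fit. The plots use every sample. T-cell and methylation results are mainly descriptive, the MRD comparison before and after response concerns responders by intent, and pharmacokinetics already has a mixed model. The assays are labelled exploratory in Section 5.6, and no decision or error rate depends on these tests. All of this stands, and it keeps the point small. It does not remove it: the sentence covers serial data with no exception and no window, so nothing prevents the poor choice.

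The End of Treatment/Relapse sample gives non-responders one more value, but at no fixed cycle, so it cannot complete a series.

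A reader might infer two stronger things. One is that the serial results will be wrong by a known percentage. The documents give no marker variance, effect or retention, and the figures in step 5 move widely with those assumptions. The other is that a mixed model would recover the all-patient change at cycle 6 and beyond. It would not: nothing scheduled is observed on non-responders after they leave, and the rebound case shows a model giving a confident wrong answer. That later samples describe patients still on treatment is a feature of the design, not a fault of the test.

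**Conclusion.** The point holds in limited form and is minor. As written, Section 9.3 permits a complete-series test that, once it includes cycle 6, uses about 4.5 to 15 of 30 patients, all responders still on treatment, and discards the remaining patients' early samples. That range rests on the plan's 30% and 50% response rates and an assumed 50% to 100% of responders still sampled. The direction, toward the responder pattern, follows from the exit rule whenever the marker tracks response. The size of any bias is illustrative only. Within baseline to cycle 3 the loss is smaller: patients who leave early and possibly early responders. The primary objective and the response rule are unaffected.

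**What to change.** Amend Section 9.3 to say:

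- Serial markers are analysed with a linear mixed model on all available samples from baseline to cycle 3. Time is a factor, on a log or logit scale where needed, with an unstructured covariance or random intercept and slope.
- A simpler covariance is named in advance as the fallback if the model does not converge.
- Results are shown by response status. Response is itself determined after baseline, so this display is descriptive.
- Cycle 6 and later are reported descriptively, labelled as patients still on treatment, with no all-patient estimate at those times.
- Friedman's test is kept as a sensitivity analysis over baseline to cycle 3.

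Sections 5.1 and 11.1 should also be reconciled with footnote i of Section 11, so that it is clear whether early responders are due cycle 2 and 3 marrow.

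The cost is a few sentences, with no added patients or samples. The downside is the assumption that values are missing at random given those observed. That is weaker than what a complete-series test needs, but it cannot be checked from the data.

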### 1.2 Secondary Objectives

- 1.2.1 To determine the composite CR rate (CR+CRi) rate in R/R AML patients who are treated with decitabine and venetoclax in combination with nivolumab.
- 1.2.2 To determine the overall response rate (CR+CRi+CRh+MLFS) rate in R/R AML patients who are treated with decitabine and venetoclax in combination with nivolumab.
- 1.2.3 To observe and record anti-tumor activity. Although the clinical benefit of this combination of drugs has not yet been established, the intent of offering this treatment is to provide a possible therapeutic benefit, and thus the patient will be carefully monitored for tumor response and symptom relief in addition to safety and tolerability.
- 1.2.4 To determine progression free survival (PFS) for R/R AML patients receiving combination therapy.
- 1.2.5 To determine the overall survival (OS) for R/R AML patients receiving this combination therapy.
- 1.2.6 To determine minimal residual disease at best response and follow throughout treatment.
- 1.2.7 To determine the frequency of GVHD including veno-occlusive disease in patients who subsequently receive allogenic transplantation after this combination therapy.
- 1.2.8 To perform pharmacokinetic (PK) and pharmacodynamics (PD) of the combination of nivolumab with decitabine plus venetoclax.

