## 2.5 Correlative Studies Background

### 2.5.1 Minimal residual disease (MRD) assessment

We propose that decitabine, venetoclax and nivolumab in combination will help achieve durable response in relapsed/refractory AML. We will be using flow cytometry (aka. immunophenotyping), cytogenetics (karyotyping along with an AML FISH panel), and next generation sequencing (NGS) to detect minimal residual disease. Minimal (ie. measurable) residual disease is defined as persistence of leukemic cells at levels below morphologic detection. In AML specifically, it can be used to assess treatment response. Furthermore, in AML the presence of MRD has strong and independent prognostic significance as patients with MRD have an increased relapse risk and decreased survival. However, this data on MRD is in relation to patients receiving standard intensive chemotherapy regimens and mostly in the upfront treatment setting. Little is known about MRD assessment utilization in patients receiving HMA/venetoclax combinations, especially in the relapsed/refractory AML setting; the most appropriate timepoint(s) to assess MRD and depth of response in relation to survival are poorly understood. Therefore, with this study we aim to gather important information on MRD assessments in patient's receiving HMA/venetoclax combinations notably in the relapsed/refractory setting. Technologies to measure MRD include immunophenotyping, cytogenetics, and mutational analysis. Utilizing NGS to monitor mutations with associated targeted therapies (*FLT3-ITD*, *IDH1/2*) and mutations with prognostic significance (*CEBPA*, *NPM1*) has been shown to be feasible in patients with

AML. Therefore, we plan to utilize NGS testing of patients' bone marrow to determine if mutant clones persists following combination therapy with decitabine, venetoclax, and nivolumab.

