## **6.6 Duration of Follow-Up**

Patients will be followed for up to 3 years after initiation of therapy or until death, whichever occurs first. Patients removed from study for unacceptable adverse event(s) will be followed until resolution or stabilization of the adverse event.

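### Section 9.3 tests MRD against an undefined disease outcome by repeated chi-square tests, which cannot support a conclusion about the best assay and time point

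*Combined protocol and SAP*

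**What the plan says.** Section 9.3 of the protocol, which holds the statistical plan, describes three MRD measures: variant allele frequency from sequencing, cytogenetics and flow cytometry. It says: "We will compare these three MRD tests at the same time points". On prognosis it says: "We will also evaluate MRD status at each time point in relation to disease outcome using chi square test of independence". The stated result is to learn "which MRD assessment(s) performed at which timepoint(s) is most meaningful and helpful in determining relapsed/refractory AML outcomes".

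The surrounding facts are these.

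- **Outcome.** Section 9.3 does not define disease outcome. Section 2.5.1 motivates MRD by relapse risk and survival, and says that the best timing and "depth of response in relation to survival are poorly understood".
- **Time points.** Section 11, footnote i: "Bone marrow biopsies will occur at the end of each cycle of induction, then every 3 cycles (starting with cycle 6) and at relapse/EOT". No last cycle is given.
- **Follow-up.** Section 6.6: "Patients will be followed for up to 3 years after initiation of therapy or until death".
- **Objective.** Section 1.2.6: "To determine minimal residual disease at best response and follow throughout treatment".
- **Status.** The biomarker plan in Section 5.6 labels the three assays exploratory. Section 9.3 calls the T-cell and methylation analyses mainly descriptive because of the small sample, but gives MRD no such caveat.

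Section 9 gives no significance level, multiplicity rule, landmark or censoring rule for the MRD tests. It names no Kaplan-Meier, log-rank or Cox method, although progression-free and overall survival are secondary objectives.

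**The concern.** A chi-square test of independence needs one complete yes-or-no outcome per patient. Relapse and survival over as much as three years are not of that kind. In a two-by-two table, a relapse at month 2 counts the same as one at month 30, and a patient whose observation stops early has no proper place.

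The patients also change from one time point to the next. Section 6.5 ends treatment at progression, loss of response or transplantation, so marrow at cycle 6 and later comes only from patients still on treatment. Without a landmark start, a stronger association at one time point than at another may reflect who was left to be tested rather than which time point is more informative.

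Finally, the plan repeats the test over assays and time points and then reads off a winner. What is at stake is that choice, which could shape how MRD is measured in later studies of this combination.

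**Working it through.** **The plan's own figures.** None are given for the MRD tests. The only error rates in Section 9 belong to the response rule (13 or more responses out of 30, 30% versus 50%). Exact binomial calculation gives 0.0845 and 0.1808, matching the printed 0.084 and 0.181. That rule is separate and unaffected.

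**1. Number of responders.** Section 2.5.1 defines MRD as disease below morphologic detection, so the tests concern patients in remission. The cited prospective study of 10-day decitabine with venetoclax (Section 2.4.1) had 13 + 10 = 23 CR/CRi among 55, or 42%. The target in Section 9.1 is 50%.

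- 30 patients at the MTD: 30 × 0.42 = 12.6 and 30 × 0.50 = 15.
- Maximum of 42 patients: 42 × 0.42 = 17.6 and 42 × 0.50 = 21.

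The range is about 13 to 21.

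**2. Expected cell counts.** Smallest expected cell = responders × smaller MRD share × smaller outcome share. A 50% event rate is assumed.

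| Responders | MRD-negative share (assumed) | Smallest expected cell |
|---|---|---|
| 15 | 50% | 15 × 0.5 × 0.5 = 3.75 |
| 15 | 30% | 15 × 0.3 × 0.5 = 2.25 |
| 21 | 50% | 21 × 0.5 × 0.5 = 5.25 |
| 21 | 30% | 21 × 0.3 × 0.5 = 3.15 |

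Only the most favourable case reaches 5.

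**3. Cost of ignoring time.** All inputs here are assumptions: 15 responders (7 MRD-negative, 8 positive), exponential relapse times with medians of 15 and 6 months (hazard ratio 2.5), follow-up 30 to 36 months, two-sided 5% level, 4000 simulated trials. At 33 months the expected share ever relapsed is 1 − 0.5^(33/15) = 78% versus 1 − 0.5^(33/6) = 98%, so most of the contrast has gone. At 12 months it is 1 − 0.5^(12/15) = 43% versus 1 − 0.5^(12/6) = 75%.

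| Method | Power, HR 2.5 | Power, HR 3 | Rejection under the null |
|---|---|---|---|
| Chi-square, ever relapsed | about 15% | about 27% | 0.3 to 0.9% |
| Chi-square, relapsed by 12 months | 23% | 29% | 4 to 5% |
| Log-rank (asymptotic) | about 35% | about 46% | about 7% |

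The log-rank advantage is real in direction, but part of it comes from a size above 5%.

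**4. Cost of ignoring censoring.** A deliberately extreme case has 21 responders, no true difference, median 8 months, 36 months of follow-up, and early censoring (mean 6 months) only in MRD-negative patients, as could happen if transplant were treated as censoring. Chi-square on observed events then rejects in 93% of trials and log-rank in 5%. This shows the mechanism, not a likely size.

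**5. Number of tests.** Three assays × four marrows (end of cycles 1, 2, 3 and 6) = 12. Adding cycles 9 and 12 gives 3 × 6 = 18. At an assumed 5% per test:

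- Independent tests: 1 − 0.95^12 = 46%; 1 − 0.95^18 = 60%.
- Simulated correlated assays and time points, 12 tests: 32 to 46% with 21 responders, 26 to 39% with 15.
- If each test rejects only 0.9% of the time, as in step 3: 1 − 0.991^12 = about 10% even under independence.

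**6. What the data can support.** For 80% power at 5% with equal groups, events needed = (1.96 + 0.84)² / (0.25 × ln(HR)²): 26 for a hazard ratio of 0.33 and 66 for 0.5. At most about 21 responders are expected.

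**The case against.** Much can be said for the plan, and several stronger readings do not hold.

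- **A reader might infer that the MRD secondary objective goes unanswered.** It does not. Objective 1.2.6 asks for MRD at best response and over treatment, not for an association with outcome. Section 9.3 serves it separately, by comparing MRD before and after response and by plotting and analysing serial data.
- **A reader might take 46% as the false-positive risk.** That figure assumes independent tests that each reject 5% of the time. The assays share patients and marrow, and chi-square on a nearly universal event rejects far less often. Both facts pull the figure down.
- **A reader might assume that nearly all patients relapse.** The documents do not say so. Section 2.1 says only that more than half of patients reaching CR relapse.
- **The outcome might be binary at a fixed time.** A chi-square or exact test could then be suitable, and a 12-month version recovers some of the lost power. The plan, however, states no such outcome.
- **The assays are labelled exploratory.** Formal multiplicity control is therefore not required. This stands, but the label does not fit with claiming to determine the best assay and time point.
- **Survival methods are underpowered too.** True. That argues for estimates and a modest claim, not for keeping chi-square.

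**Conclusion.** The concern holds in a limited form. The outcome is undefined. If it is relapse, progression-free or overall survival, the named test discards event times, mishandles censoring, compares differently selected groups at later time points and rests on expected counts mostly below 5.

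Under the assumed relapse times, power is about 15% against about 35% for log-rank, with the caveat on log-rank size. The roughly 32 to 46% chance of at least one false positive in 12 correlated tests assumes a nominal 5% level, about half the patients having an event, and 21 responders. It is lower with fewer responders or where chi-square is conservative. The hazards, MRD split and significance level are not in the documents.

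The unreliable part is the conclusion about which assay and time point is best. The safety objective, the MTD and the 13-of-30 response rule do not depend on it. The change is worth making because it is cheap and the stated claim exceeds what about 20 responders can show under any method.

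**What to change.** Rewrite the MRD paragraph of Section 9.3, using the same data:

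1. Define disease outcome, for example relapse-free survival and overall survival.
2. At each marrow time point, start a landmark analysis among patients then at risk and assessed. Report Kaplan-Meier curves by MRD status and Cox hazard ratios with confidence intervals. If a p-value is given, use an exact or permutation log-rank test.
3. State the censoring rule, including how transplant is handled in the analysis.
4. Use Fisher's exact test only for binary outcomes at a fixed time.
5. Name one main assay and landmark, and label the rest exploratory.
6. Replace *determine* with *explore*.

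The cost is slightly more analysis work and a more modest stated conclusion. No extra samples, visits or patients are needed.
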